## 3.3 Study Duration, Enrollment and Number of Sites

## 3.3.1 Duration of Subject Study Participation

The study duration per subject will be from the time of their cardiac arrest through hospital discharge or death. Subjects alive 30 days after the end of the 4.25 year enrollment period will have their final outcome data assessed at that time.

## 3.3.2 Total Number of Study Sites/Total Number of Subjects Projected

The study will be conducted at approximately 20 investigative sites in the United States.

Recruitment will stop when approximately 1530 subjects are enrolled. As per the study design, enrollment will end 4.25 years from study start.

# 3.4 Study Population

# 3.4.1 Subject Inclusion Criteria

All children  $\ge$ 37 weeks corrected gestational age and <18 years old with an invasive airway in place at the time of a cardiac arrest or who had an airway placed during the first 5 minutes of CPR, and who required at least 1 minute of CPR.

## 3.4.2 Subject Exclusion Criteria

- 1) Lack of commitment to aggressive ICU therapies (e.g., CPR performed as part of end-of -life care as documented in the medical record)
- 2) Brain death determination prior to the CPR event
- 3) The admission to the hospital was secondary to an out-of-hospital CPR event (known poor outcomes if there is a recurrent arrest)
- 4) Supported by Veno-Arterial ECMO at the start of CPR

Healthcare provider inclusion criteria: bedside care providers of all disciplines working in ICU

Exclusion criteria: none

Subjects that do not meet all of the enrollment criteria may not be enrolled. Any violations of these criteria must be reported in accordance with IRB Policies and Procedures.

#### 4 STUDY PROCEDURES

Standard cardiac arrest data (e.g., demographics, intra- and post-arrest physiologic variables, CPR quality variables) will be collected on all subjects, extracted from the electronic medical record, continuous bedside monitors, and other patient physiologic monitoring devices (e.g., NIRS). Data elements to be collected from the pre-, intra-, and post-arrest periods include but are not limited to:

Patient Characteristics: date of birth; sex; race/ethnicity; height; weight; illness category (medical cardiac, medical non-cardiac, surgical cardiac, surgical non-cardiac, trauma). Pre-existing conditions: respiratory insufficiency; hypotension; congestive heart failure; pneumonia; sepsis; trauma; renal insufficiency; malignancy; congenital heart disease, if yes, single ventricle; if single ventricle, the anatomy is specified; if surgical palliation completed, type of most recent surgical procedure is noted (Norwood with Sano modification, Norwood with modified BT shunt, Hybrid Procedure, Bi-directional Glenn, Fontan, other); vasoactive inotropic scores (2 hours preceding CPR); pediatric cerebral performance category (PCPC) score; functional status scale (FSS) score.

CPR Event Characteristics: interventions at CPR start (e.g., vasoactive infusion); immediate cause of arrest (Y/N for hypotension, respiratory decompensation, arrhythmia, cyanosis without respiratory decompensation); first documented rhythm requiring CPR; time of first shockable rhythm; pre-shock pause (seconds); time of first defibrillation; time of first vasopressor administration for non-shockable rhythm; drug interventions during CPR; duration of CPR (minutes). CPR mechanics variables: Compression depth (mm); rate (per minute); chest compression fraction; and leaning during relaxation phase (release velocity, if available [mm/second]). Ventilation variables: ETCO2 (mmHg); ventilation rate (bpm); airway opening index; other ventilation variables as available (e.g., Peak Inspiratory Pressure [cmH2O]). Intra-arrest physiology (arterial BP (mmHg), ETCO2 (mmHg), and arterial/venous blood gases.

Post-cardiac Arrest Care Variables (first 6 and >6-24 hours post-arrest with highest and lowest unless indicated): systolic and diastolic arterial BP (mmHg); temperature (°C); arterial PaO2 (mmHg); PaCO2 (mmHg); pH; highest lactate (mmol/L); glucose (mg/dL); vasoactive scores (6, 12 and 24 hours); required extracorporeal membrane oxygenation (ECMO) support (Y/N); targeted temperature management (TTM, Y/N); if TTM, goal max temperature; electroencephalography (EEG; Y/N).

ICU Care Providers: No identifying information will be collected from the providers working in the ICUs who may be targeted with the training intervention. During bedside trainings described below, only shift (AM [7am to 7pm], PM [7pm to 7am]), discipline (MD, RN, RT, other) and time since last training (<1 week, <1 month, >3 months) will be recorded. These variables are used to be able to describe the spread of the *OPTI-VENT* training.

#### 5 STUDY EVALUATIONS AND MEASUREMENTS

#### 5.1 Screening and Monitoring Evaluations and Measurements

#### 5.1.1 Medical Record Review

All data elements to be collected are entered into the electronic medical record as part of routine clinical care.

#### 5.2 Cardiac Arrest Event Data:

Data recorded during the chest compression event include but are not limited to those listed in Section 4.

#### 5.3 Patient Characteristics

Patient characteristics to be collected include but are not limited to those listed in Section 4. The only PHI data collected will be subject name, MRN, date of birth, and date of the event, which will be kept confidential in accordance with Institutional policies and HIPAA IRB regulations. The only PHI that will be entered into REDCap database will be date of birth and date of arrest.

### 5.4 Post-Resuscitation Phase

Data elements to be collected include but are not limited to those outlined in Section 4.

## 5.5 Efficacy Evaluations

The primary outcome is survival to hospital discharge with favorable neurologic outcome, defined as a PCPC score of 1-2 or no change from baseline.

Secondary outcomes will be:

- survival to discharge
- Return of spontaneous circulation (ROSC) >20 minutes
- Return of circulation with ECMO support
- Substantive new morbidity among survivors (increase in Functional Status Scale score ≥3)
- Intra-arrest cerebral oxygen saturation (%) as measured by Near Infrared Spectroscopy (NIRS) monitors, as part of standard clinical care in the pedRES-Q sites.
- Proportion of events 1) that achieve the DBP recommended thresholds during CPR (14), and
   2) with either hyperoxia (PaO2 >300 mmHg) or hypocarbia (PaCO2 <30 mmHg) in the immediate post-arrest period (15).

#### 5.5.1 Diagnostic Tests, Scales, Measures, etc.

Table 1: Pediatric Cerebral Performance Category (from medical record review)(16)

core	Category	Description
1	Normal	Age-appropriate level of functioning In preschool-aged children, appropriate development In school-aged children, attendance in regular classes
2	Mild disability	Can interact at an age-appropriate level Minor neurologic disease that is controlled and does not interfere with daily functioning (eg, seizure disorder) In preschool-aged children, possibly minor developmental delays, but with > 75% of all daily living developmental milestones above the 10th percentile In school-aged children, attendance in regular school but in a grade that is not appropriate for age or in the appropriate grade but failing because of cognitive difficulties
3	Moderate disability	Below age-appropriate functioning  Neurologic disease that is not controlled and severely limits activities  In preschool-aged children, most daily living developmental milestones below the 10th percentile  In school-aged children, can do ADLs but attend special classes because of cognitive difficulties or a learning deficit
4	Severe disability	In preschool-aged children, ADLs milestones below the 10th percentile and excessive dependence on others for activities of daily living In school-aged children, possibly severe impairment that prevents school attendance and dependence on others for ADLs In preschool-aged and school-aged children, possibly abnormal motor movements, including nonpurposeful, decorticate, or decerebrate responses to pain
5	Coma or vegetative state	Unawareness
6	Death	-
		for any single criterion is used for categorizing. Deficits are scored only if they result from a neurologic disorder. Assessments or an interview with the caretaker.
Adapted	d from Fiser DH . Assess	sing the outcome of pediatric intensive care. J Pediatr 121(1):68-74, 1992. doi:10.1016/s0022-3476(05)82544-2

Table 2: Functional Status Scale Score (from medical record review)(17)

	Normal (Score = 1)	Mild Dysfunction (Score = 2)	Moderate Dysfunction (Score = 3)	Severe Dysfunction (Score = 4)	Very Severe Dysfunction (Score = 5)
Mental status	Normal sleep/wake periods; appropriate responsiveness	Sleepy but arousable to noise/touch/movement and/or periods of social nonresponsiveness	Lethargic and/or irritable	Minimal arousal to stimuli (stupor)	Unresponsive, coma, and/or vegetative state
Sensory functioning	Intact hearing and vision and responsive to touch	Suspected hearing or vision loss	Not reactive to auditory stimuli or to visual stimuli	Not reactive to auditory stimuli and to visual stimuli	Abnormal responses to pain or touch
Communication	Appropriate noncrying vocalizations, interactive facial expressiveness, or gestures	Diminished vocalization, facial expression, and/ or social responsiveness	Absence of attention- getting behavior	No demonstration of discomfort	Absence of communication
Motor functioning	Coordinated body movements, normal muscle control, and awareness of action and reason	1 limb functionally impaired	≥2 limbs functionally impaired	Poor head control	Diffuse spasticity, paralysis, or decerebrate/decorticate posturing
Feeding	All food taken by mouth with age-appropriate help	Nothing by mouth or need for age-inappropriate help with feeding	Oral and tube feedings	Parenteral nutrition with oral or tube feedings	All parenteral nutrition
Respiratory status	Room air and no artificial support or aids	Oxygen treatment and/or suctioning	Tracheostomy	Continuous positive airway pressure treatment for all or part of the day and/ or mechanical ventilatory support for part of the day	Mechanical ventilatory support for all of the day and night

# **6 STATISTICAL CONSIDERATIONS**

# 6.1 Primary Endpoint

The primary outcome is survival to hospital discharge with favorable neurologic outcome, defined as a PCPC score of 1-2 or no change from baseline. Baseline will be defined as the child's pre-

admission status. For those children hospitalized more than 90 days at the time of their CPR event, a new "baseline" will be assessed at least 30 days prior to the CPR event.

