#### **Study Interventions and Measures:**

Standard cardiac arrest data collection will be completed for cardiac arrest subjects from the electronic medical record, continuous bedside monitors, and other patient physiologic monitoring devices (e.g., near infrared spectroscopy [NIRS]) for pre-, intra-. and post-arrest time periods.

The primary outcome is survival to hospital discharge with favorable neurologic outcome, defined as a Pediatric Cerebral Performance Category score of 1-2 or no change from baseline. Secondary outcomes will be survival to discharge, return of spontaneous circulation (ROSC) >20 minutes, return of circulation (ROC) with extracorporeal support, substantive new morbidity among survivors (increase in Functional Status Scale score  $\geq$ 3), intra-arrest cerebral oxygen saturation, and proportion of events 1) that achieve diastolic blood pressure (DBP) thresholds during CPR, and 2) with either hyperoxia or hypocarbia in the immediate post-arrest period.

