# **PROTOCOL SYNOPSIS**

Study Title	OPTImal Ventilation to Improve Cardiac Arrest Outcomes			
	^			
Funder	National Institute of Child Health and Human Development			
Clinical Phase	NA			
Study Rationale	In 2020, the American Heart Association (AHA) increased the recommended CPR ventilation rate from 10 breaths per minute (bpm) to a range of 20 – 30 bpm, a target associated with better outcomes. Unfortunately, providers do not achieve this recommended target in actual practice. As such, innovative training strategies to this CPR parameter are potential therapeutic interventions to rescue more children from cardiac arrest. To that end, we developed an OPTImizing VENTilation ( OPTI-VENT ) bundle consisting of provider education and point-of-care CPR ventilation rate guidance (CPR cue cards and a ventilation rate metronome). Our bundle demonstrated efficacy to train providers to a specific ventilation rate with high compliance. In this protocol, we describe an adaptive, parallel-stepped-wedge hybrid cluster-randomized trial to determine if the OPTI-VENT bundle can improve cardiac arrest outcomes by training providers to the 2020 CPR ventilation rate.			
Study Objective(s)	Primary			
	• To evaluate the effectiveness of the OPTI-VENT bundle to improve survival to discharge with favorable neurological outcome (Pediatric Cerebral Performance Category Score 1-2 or no change from baseline) among children receiving at least 1 minute of CPR.			
	Secondary Analytic Observational Objectives			
	• Determine if there is an alternative ventilation rate that is associated with improved 1) survival outcomes and 2) intra-arrest physiology (e.g., blood pressure).			
	• Determine the association between Airway Opening Index (a newly discovered ventilation metric) and 1) survival outcomes, and 2) intra- arrest physiology (e.g., blood pressure and exhaled carbon dioxide)			
	
 
Determine if AOI can be modified by changing airway pressures delivered during CPR using novel multidimensional machine learning algorithms.
 
			
Test Article(s)	OPTI-VENT QI Bundle Description:			

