# 6.2 Secondary Endpoints

Secondary outcomes will be:

- Survival to discharge, a binary indicator of whether or not the subject was discharged alive.
- Return of spontaneous circulation (ROSC) >20 minutes, a binary indicator of whether or not the subject achieved adequate circulation via a native heartbeat.
- Return of circulation with extracorporeal membrane oxygenation (ECMO) support, a binary indicator that adequate circulation could only be achieved with ECMO support (i.e., E-CPR).
- Substantive new morbidity among survivors (increase in Functional Status Scale score ≥3).
- Intra-arrest cerebral oxygen saturation (%) as measured by Near Infrared Spectroscopy (NIRS) monitors, as part of standard clinical care in the pedRES-Q sites.
- Proportion of events 1) that achieve the DBP thresholds during CPR (14), and 2) with either hyperoxia (PaO2 >300 mmHg) or hypocarbia (PaCO2 <30 mmHg) in the post-arrest period (15).

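### The primary outcome's 'no change from baseline' branch scores a survivor who improves from PCPC 4 or 5 but stays at 3 or 4 as unfavourable, while a child with the same baseline who does not improve is favourable

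*Protocol*

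**What the plan says.** Protocol section 6.1 gives the primary outcome as survival to discharge with a favourable neurological outcome, "defined as a PCPC score of 1-2 or no change from baseline". Section 5.5 and the efficacy row of the Protocol Synopsis use the same words. The synopsis objective has "Pediatric Cerebral Performance Category Score 1-2 or no change from baseline", and the abstract (Study Interventions and Measures) has "defined as a Pediatric Cerebral Performance Category score of 1-2 or no change from baseline". All five places agree, and none gives a direction of change.

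Baseline is the child's status before admission. For a child in hospital for more than 90 days at the time of the event, section 6.1 substitutes a new baseline that "will be assessed at least 30 days prior to the CPR event".

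Table 1 in section 5.5.1 sets out PCPC as an ordered scale from 1 (normal) to 6 (death). Category 5, the worst a survivor can have, is "Coma or vegetative state". The only neurological exclusion in section 3.4.2 is "Brain death determination prior to the CPR event", so children with baseline PCPC 3, 4 or 5 can be enrolled.

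**The concern.** On a scale where higher is worse, 'no change' and 'no worsening' are different rules. They part when a child with a poor baseline leaves hospital better than baseline but still outside categories 1-2. Under 'no change' that child meets neither branch and is unfavourable, while a child with the same baseline who shows no gain is favourable.

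'No worsening' was probably meant, but the protocol does not say so anywhere. Where it wants a direction it gives one: the Functional Status Scale outcome in section 6.2 counts only an increase of at least 3 points. A programmer who derives the primary outcome from a change score of zero will get a different variable from one who assumes the likely intent. At stake is an unambiguous, correctly ordered primary endpoint, which also feeds the formal efficacy looks at 2, 3 and 4.25 years (section 6.5).

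**Working it through.** No figure in the protocol depends on this point, so there is nothing of the plan's to reproduce. The check is an enumeration followed by a range for size.

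**1. Two rules for survivors.** Let b be baseline PCPC and d discharge PCPC, each from 1 to 5.

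- As written: favourable if d ≤ 2 or d = b.
- No worsening: favourable if d ≤ 2 or d ≤ b.

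**2. All 5 × 5 = 25 pairs.**

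| Group of pairs | Number | As written | No worsening |
|---|---|---|---|
| Discharge 1 or 2, any baseline | 10 | favourable | favourable |
| 3 to 3, 4 to 4, 5 to 5 | 3 | favourable | favourable |
| Worsening to 3, 4 or 5 | 9 | unfavourable | unfavourable |
| 4 to 3, 5 to 3, 5 to 4 | 3 | **unfavourable** | **favourable** |

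The total is 10 + 3 + 9 + 3 = 25. The rules differ in the last row only. Any improvement from baseline 3 ends in category 1 or 2 and is favourable under both rules, so only baselines 4 and 5 are exposed.

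**3. Size.** The documents give neither the distribution of baseline PCPC nor the frequency of improvement. Two assumptions are needed:

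- share of subjects with baseline PCPC 4-5: 5% to 15%;
- share of those who survive improved but remain at 3 or 4: 1% to 3%.

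Misclassified share = product of the two:

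- low: 0.05 × 0.01 = 0.0005, or 0.05%;
- high: 0.15 × 0.03 = 0.0045, or 0.45%.

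Section 6.4 expects 1500 index events for analysis:

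- low: 1500 × 0.0005 = 0.75, about 1;
- high: 1500 × 0.0045 = 6.75, about 7.

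**4. Scale against the design effect.** The smallest scenario in section 6.4 is a 12-point gain when the target rate is achieved, with 85% compliance under intervention and 20% under control. The difference between arms is then (0.85 − 0.20) × 12 = 7.8 percentage points. A misclassified share of at most 0.45 percentage points, under a rule applied alike in both arms, is small beside that.

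**The case against.** The best reply is that this is loose wording with an obvious intent, that coding of a derived endpoint is usually settled in the SAP (not at hand), and that the affected children are very few. The last part stands, and it limits the size of the point. The rest does not remove it. The protocol does not leave the rule open but fixes it in five places. An SAP that uses 'no worsening' would depart from the protocol's text, and one that follows the text would code the misordering.

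A reader might infer four stronger things, which the documents do not support.

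- *Any benefit to children with prior disability counts against the bundle.* It does not. For a child with baseline 4, survival at 4 instead of death, discharge at 4 instead of 5, and survival at 1-2 are all credited. A child who would have died and instead leaves at 3 goes uncounted, which is neutral. Only a shift from 'unchanged' to 'improved but still at 3 or 4' is penalised.
- *All children with baseline 3 or worse are exposed.* The enumeration shows that baseline 3 is not.
- *The re-baselining after 90 days makes improvement likely, because critical illness depresses the new baseline.* The note to Table 1 limits scored deficits to those of neurological origin, so general critical illness should not lower the score. A new neurological injury in hospital could, but no frequency is given. For all other children, improvement means leaving hospital neurologically better than before admission.
- *The treatment comparison is biased.* The rule is the same in both arms, and nothing in the documents shows that these children fall unevenly between them.

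That an improved child is scored together with deaths adds nothing in itself. Any binary composite does the same to survivors who worsen.

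**Conclusion.** The point holds as a defect in the stated definition of the primary outcome. The rule as written misorders three survivor pairs (4 to 3, 5 to 3 and 5 to 4), and nothing else in the protocol corrects this. The effect is probably very small: the range of 1-7 events rests wholly on the two assumed shares and would move in proportion to them. It is a low-impact correction, and it does not suggest that the primary analysis will mislead. It is worth making because it concerns the primary endpoint, and because settling the wording once outcomes have been seen would be a post hoc change.

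**What to change.** In the abstract, the synopsis objective, the synopsis efficacy row, section 5.5 and section 6.1, replace the phrase with: *alive at discharge with PCPC 1-2 or no worsening from baseline (discharge PCPC less than or equal to baseline PCPC)*. Make the change before the first formal efficacy look at 2 years, and use the same rule in the SAP and in the code that derives the endpoint.

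The cost is one phrase in an amendment. Baseline PCPC is already among the data elements in section 4, and discharge PCPC is already needed for the outcome. No new data, change in sample size or change in conduct is required.

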# 6.2 Secondary Endpoints

Secondary outcomes will be:

- Survival to discharge, a binary indicator of whether or not the subject was discharged alive.
- Return of spontaneous circulation (ROSC) >20 minutes, a binary indicator of whether or not the subject achieved adequate circulation via a native heartbeat.
- Return of circulation with extracorporeal membrane oxygenation (ECMO) support, a binary indicator that adequate circulation could only be achieved with ECMO support (i.e., E-CPR).
- Substantive new morbidity among survivors (increase in Functional Status Scale score ≥3).
- Intra-arrest cerebral oxygen saturation (%) as measured by Near Infrared Spectroscopy (NIRS) monitors, as part of standard clinical care in the pedRES-Q sites.
- Proportion of events 1) that achieve the DBP thresholds during CPR (14), and 2) with either hyperoxia (PaO2 >300 mmHg) or hypocarbia (PaCO2 <30 mmHg) in the post-arrest period (15).

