#### 1.4 Relevant Literature and Data

**Background:** Of the >15,000 US children who have a pediatric in-hospital cardiac arrest (p-IHCA) each year, only ~40% survive (1). Interventions to improve CPR quality can save lives, but to date, there is a research imbalance, with much more of a focus on optimal chest compression techniques as compared to ventilation strategies. Using data extrapolated from adult studies, previous iterations of CPR Guidelines recommended a ventilation rate of 10 bpm for both children and adults. This recommendation was based upon the concern that higher ventilation rates would detrimentally affect hemodynamics during pediatric CPR as well (i.e., decreased venous return from increased intrathoracic pressure)(10, 11). In contrast, our NIH-funded multicenter observational data found that higher ventilation rates were beneficial to children (6). As a result, in 2020, the AHA increased the CPR ventilation rate from 10 bpm to 20 – 30 bpm. Due to the small number of patients and observational nature of our preliminary work, there remains intense controversy across the seven international resuscitation councils (e.g., AHA, European Resuscitation Council [ERC]) regarding optimal pediatric CPR ventilation rates. While the AHA recommends 20 - 30 bpm, the ERC recommends a range of 10-25 bpm (25 bpm for infants down to 10 bpm for anyone over 12 years). All councils classify their pediatric ventilation rate recommendation as "weak," with "very low level of evidence," and list ventilation rate as a research gap that requires high priority multicenter evidence to inform future guidelines.

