## 2.1 Primary Objective (or Aim)

The primary objective of this study is to determine the effectiveness of the *OPTI-VENT* bundle to improve survival to discharge with favorable neurological outcome among children receiving at least 1 minute of CPR.

In embedded observational studies, the secondary objectives are to:

- Determine if there is an alternative ventilation rate that is associated with improved 1) survival outcomes and 2) intra-arrest physiology (e.g., blood pressure).
- Determine the association between Airway Opening Index and 1) survival outcomes and 2) intra-arrest physiology (e.g., blood pressure and exhaled carbon dioxide)
- Determine if AOI can be modified by changing airway pressures delivered during CPR using novel multidimensional machine learning algorithms.

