## 6.4 Sample Size and Power

Primary Objective (Efficacy of OPTI-VENT bundle)

Based on pediRES-Q data, ~360 index CPR events are expected to occur annually. After excluding ~7 events/year that occur during transition periods, 1500 index events will be available for analysis. In our preliminary work, rates consistent with 2020 AHA Guidelines were associated with

	Compliance with Ventilation Rate Target (20 – 30 bpm)			
Absolute improvement in survival with favorable neurologic outcome	85%	90%	95%	
12%	70%	76%	82%	
14%	82%	87%	91%	
16%	91%	94%	97%	

an improvement in survival with favorable neurologic outcome of >20 percentage points. Understanding that it is likely that the magnitude of the effect will be smaller in a multicenter study, we have provided estimated power to detect a 12-16% improvement when

the target rate is achieved compared to a baseline rate of survival with favorable neurologic outcome of 30% (data obtained from an existing pediRES-Q online real-time dashboard) when the target rate is not achieved. We also show the impact of the level of compliance with the target rate that we can achieve in the intervention group compared to a control group rate of 20%. We have assumed an intra-cluster correlation of 2% (based on our prior IHCA data). To ensure adequate power, we have included a pre-planned adaptive design. If after 12 months of enrollment, sites are enrolling ≤90% of expected, we will add 6 additional ICUs. If they are enrolling ≤75% of expected, we will add an additional 10 ICUs. As the pediRES-Q network has more than 50 active domestic / international sites, recruiting 10 sites is feasible. New sites if added will all begin in the control group starting at 14 months and will randomly be assigned a transition time according to a standard stepped-wedge design. Start-up within 2 months is feasible due to these sites starting in control, our plan for continuous enrollment monitoring, and the infrastructure of the pediRES-Q network (active IRBs and DUAs). Our design adaptation can also be used to mitigate power issues due to unexpectedly high baseline compliance in the control group or inability to achieve compliance training targets in the interventional group.

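### New functional morbidity is compared only among survivors, a group the bundle is meant to change, so the contrast is not protected by randomisation and can be biased in either direction

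*Protocol*

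**What the plan says.** The Abstract, Section 5.5 and Section 6.2 all restrict the Functional Status Scale (FSS) outcome to children who survive. Section 6.2 words it as "Substantive new morbidity among survivors (increase in Functional Status Scale score ≥3", and Section 5.5 likewise begins the item with "Substantive new morbidity among survivors". The three places agree with one another. None offers a version in which deaths are counted.

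Section 6.2 also lists "Survival to discharge, a binary indicator of whether or not the subject was discharged alive" as a separate secondary outcome. The primary objective in Section 2.1 is to "improve survival to discharge with favorable neurological outcome among children receiving at least 1 minute of CPR". Section 6.3 analyses the primary outcome in all index events outside the transition periods and gives a model for that outcome only. The protocol does not say how the survivors-only comparison should be read.

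**The concern.** The denominator of the FSS outcome is fixed after assignment, by an event the bundle is intended to influence. If the bundle works, its survivors include children who would have died under control, and the control arm has no counterpart for them. A difference in new morbidity between the two survivor groups then mixes two things: any effect of the bundle on children who survive either way, and the change in who survives. Adjusting for illness category, age, rhythm and time would not in general separate them, because survival also depends on severity that is not measured.

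FSS covers ground that the other outcomes do not. According to the note to Table 1, PCPC counts deficits only when they are of neurologic origin. Table 2 shows that FSS also scores feeding and respiratory status. Sections 6.5 and 8.1 say that adverse events are not collected. FSS change is therefore the only listed outcome that captures non-neurologic functional morbidity, and if its sign misleads, no other listed outcome corrects it in that domain.

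**Working it through.** The protocol gives no figure for this outcome, so there is none to reproduce. What follows shows what the survivor restriction can do.

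**Inputs**
- Control survival S0 = 40%, the approximate figure for paediatric in-hospital arrest in Section 1.4.
- Extra survivors e = 8.4 points. This is an assumption, borrowed from the primary outcome in Section 6.4: a 12-point effect at 90% compliance against 20% in control, so 0.12 × (0.90 − 0.20) = 0.084. The implied rates are 0.30 + 0.20 × 0.12 = 32.4% and 0.30 + 0.90 × 0.12 = 40.8%. They give 76.3% power against the 76% in the protocol's table, using a hybrid-design variance with intra-cluster correlation 0.02, assumed step timing and no time effects. That supports the reading of 8.4 points as the planned difference. It does not show that survival will rise by that amount.
- New morbidity among children who survive either way, q0 = 20% (assumed).
- New morbidity among extra survivors, q1 (assumed and varied).
- No child who would survive under control is harmed or helped.

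**Formulas**
- Survivor morbidity under the bundle = (S0·q0 + e·q1) / (S0 + e)
- Death or new morbidity under control = 1 − S0(1 − q0) = 1 − 0.40 × 0.80 = 68.0%
- Death or new morbidity under the bundle = 1 − S0(1 − q0) − e(1 − q1)

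**Results (control survivor morbidity 20.0%)**

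| q1 | Survivor morbidity, bundle | Change | Death or new morbidity, bundle |
|---|---|---|---|
| 10% | (0.080 + 0.0084)/0.484 = 18.3% | −1.7 points | 60.4% |
| 20% | (0.080 + 0.0168)/0.484 = 20.0% | 0 | 61.3% |
| 50% | (0.080 + 0.0420)/0.484 = 25.2% | +5.2 points, OR 1.35 | 63.8% |
| 70% | (0.080 + 0.0588)/0.484 = 28.7% | +8.7 points, OR 1.61 | 65.5% |

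The sign of the survivor contrast follows the sign of q1 − q0. The composite falls by e(1 − q1) in every row, as it must when survivors are added and nobody is harmed.

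**Range when q1 exceeds q0.** With S0 from 40% to 50%, q0 from 20% to 30%, e from 5 to 12 points and q1 from 50% to 70%, the apparent worsening runs from +1.8 to +11.5 points (OR 1.09 to 1.84).

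**Chance of a nominally significant result.** Section 6.4 says "1500 index events will be available for analysis", or about 750 per condition if split equally. Ignoring clustering, the +5.2 and +8.7 point rows would reach two-sided 0.05 with probability about 35% and 73%.

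**Mirror case.** Suppose the bundle lost 5 points of survival, all among children with 50% morbidity. Survivor morbidity would read (0.080 − 0.025)/0.35 = 15.7%, which looks better than 20.0%, while death or new morbidity would rise to 1 − (0.320 − 0.025) = 70.5%.

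**Direction on the protocol's own neurologic scale.** Taking 40% survival and the "baseline rate of survival with favorable neurologic outcome of 30" per cent from Section 6.4, 10 of every 40 control survivors (25%) have an unfavorable PCPC outcome. Adding 8.4 points of favorable survivors gives 10/48.4 = 20.7%. Using the implied control rate of 32.4% instead gives 7.6/40 = 19.0% and 7.6/48.4 = 15.7%. On PCPC, then, the planned scenario makes survivors look better, not worse.

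**Limits of the composite.** In the main scenario deaths make up 60/68.0 = 88% of control composite events. With 45% control survival and 30% morbidity they make up 55/68.5 = 80%. Survival gains can hide functional harm: at 48.4% survival the composite stays at or below 68.0% until survivor morbidity passes (0.680 − 0.516)/0.484 = 33.9%, up from 20%.

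**The case against.** A reader might infer that the extra survivors are probably the sicker children, so that a beneficial bundle will tend to be reported as increasing morbidity. The documents do not support that. The planned gain is in survival with favorable neurologic outcome, and the PCPC arithmetic above points the other way. FSS can diverge from PCPC because it includes feeding and respiratory items, but its mental status, communication and motor items overlap with neurologic function, and the protocol gives no FSS rate for any group. This objection stands: the direction is open.

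The primary outcome counts death as failure over all index events, survival to discharge is reported separately, and the interim monitoring rules do not mention FSS. A reader who looks at all three results is partly protected. That also stands and keeps the point minor. It does not supply a randomised comparison on functional morbidity, and a survivors-only odds ratio can be quoted alone.

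The testing and caveats for secondary outcomes may be in a statistical analysis plan that is not shown. That is fair for the method. The survivor population, however, is part of the outcome definition, and the protocol fixes it in three places.

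Finally, a composite that is mostly deaths largely repeats the survival outcome and can conceal harm. This stands against replacing the survivor outcome, but not against adding the composite beside it.

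**Conclusion.** The concern holds as a limitation of one secondary outcome. The survivors-only FSS contrast conditions on something the bundle is meant to change, so randomisation does not protect it. It can mislead in either direction and is unbiased only if extra survivors carry the same new-morbidity rate as the others. The sizes shown, from −1.7 to +8.7 points in the main scenario and up to +11.5 points across the wider range, are illustrations. Only the 40% survival figure is taken directly from the protocol. The gain of 8.4 points is borrowed from the primary outcome, and both morbidity rates are assumed. The primary outcome and the sample size are unaffected.

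**What to change.** In Sections 5.5 and 6.2 and the Abstract, add a secondary outcome defined over all analysed index events: death before discharge or an FSS increase of 3 or more. Name it as the outcome for between-group inference on functional morbidity. For children still in hospital 30 days after enrollment ends, use the assessment already set for that point in Section 3.3.1. Keep the survivors-only FSS result, report it next to the composite and survival to discharge, and label it as a non-randomised comparison.

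The cost is one derived variable from data already planned for collection, with no change to the primary analysis or the sample size. The drawback is that the composite is driven largely by death, overlaps with survival to discharge and can mask functional harm, which is why the survivor figure has to stay.
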